6. HUMAN SUBJECT CONSIDERATIONS

6.1 Anticipated Benefits

ReCell is designed to provide an environment to enhance skin regeneration, and to facilitate rapid wound healing, providing the potential to eliminate or minimize scar formation. By introducing an autologous epidermal cell suspension onto a wound surface, the ReCell technology takes advantage of, and enhances, the body's natural regenerative response to heal itself.

Wounded service members frequently possess limited donor site availability due to the nature and extent of associated injuries and therefore harvest sites for the split-thickness skin grafting is often limited. The ReCell Autologous Cell Harvesting System (ReCell device) allows autologous transplant of the patient's own skin cells, including epidermal progenitor cells using a small thin biopsy site (typically no larger than 2 cm by 2 cm). Used in combination with a meshed split-thickness skin graft (STSG) over INTEGRA™ MBWM, ReCell should allow for an expanded meshing ratio, thereby decreasing the required donor site. With the direct application of autologous epidermal progenitor cells the technology also offers the potential to promote faster healing, minimization of mesh patterned scar and improved patient quality of life.

ReCell has been demonstrated to deliver viable keratinocytes, melanocytes, fibroblasts and Langerhans cells to the wound surface. Preliminary clinical data demonstrate that wounds treated with ReCell rapidly re-epithelialize with reduction of systemic effects, wound infection or adverse reactions, yield improved scar texture, reduce contracture, heal free of erythema and achieve re-pigmentation at the treatment site.

Subjects participating in this clinical research trial may or may not derive a direct benefit from study participation. Although we cannot guarantee a positive outcome from this research project, validating the safety and preliminary efficacy of this treatment could provide a new approach in regenerative medicine. Increased knowledge and technological advancement may result from the conduct of this research study and potentially help a large number of individuals in the future.

6.2 Risks and Discomforts

Subjects will be monitored for safety from time of enrollment to conclusion of study visits. All adverse events will be collected by direct subject communication with investigator/study coordinator and review of source documents.

Any conditions or symptoms reported after the subject receives investigational product will be recorded as an adverse event (AE) on the AE eCRF. This includes new events after study device administration, conditions that become more severe or increase in frequency, any disease-related signs or symptoms present at the Screening Pre-Treatment visit that have worsen in severity or frequency, as well as any event or finding that the Investigator feels is clinically significant.

At each post-treatment visit, subjects will be asked by the PI and/or AI about any AE's

they have experienced since the previous visit. Any adverse condition or symptom reported will be reported and recorded as an AE in the subject's source documents and on the AE eCRF page. The subject will be instructed to contact the study site in the event they experience any significant AE's. At the discretion of the Investigator, the subject may be asked to come to the study site for an unscheduled visit.

There are no known risks of the ReCell device based on results from over 5,000-treatment procedures conducted worldwide. Potential risks to the volunteer that will be monitored may include: delayed healing/non-healing of wound and donor site, graft loss or rejection, heterotopic ossification, infection, scar contracture, durability (i.e. abrasions/injuries at graft site due to graft fragility), allergic response to trypsin, and other treatment-related adverse events requiring surgical intervention prior to 12 weeks post-treatment.

- Rare but serious (Event Rate < 1%)
 - Death, side effects and complications from anesthesia, allergic response to trypsin, allergic response to lidocaine used prior to the biopsy procedure and radiation exposure for radiographic imaging for assessment of heterotopic ossification
- Less Likely (1% ≤ Event Rate < 5%)
 - Keloid formation, infection at wound site or donor sites, reduced or loss of skin sensation or increased sensitivity, scarring, skin discoloration, uneven skin surface
- Likely (5% ≤ Event Rate < 10%)
 - Discomfort, bruising, bleeding with phlebotomy at site of blood draw and/or punch biopsy, scar contractures that impact limb function, total graft loss
- More likely (Event Rate ≥ 10%)
 - Heterotopic ossification, partial graft loss. Greater than 65% of combat casualties develop heterotopic ossification as a result of their injuries. A number of wounds may develop HO as a result of the initial trauma and not directly caused by the application of STSG or ReCell spray skin.

Risk Analysis

Anticipated Risks

The potential risks to the subject arising from the biopsy collection and grafting procedures, and from exposure to the ReCell Device, are analyzed in the tables below.

Risks and Mitigation Strategies for ReCell® Autologous Cell Harvesting Device

Potential Risks	Mitigation Strategies
-----------------	-----------------------

Allergic reaction to anesthesia, medications, or device	
 Enrollment will be restricted to subjects with no known allergies to study materials (device, anesthesia, and/or medications) Post-operative assessment of allergic response performed throughout the study period
Viral transfer from animal enzyme	
 Trypsin has been extensively tested for viruses and undergone viral elimination processes which have been validated
Potential Risks	Mitigation Strategies
Risks related to tissue response at Donor and Treatment Sites	
Infection	
 Instructions for use (IFU) detail wound bed preparation procedures Patients with active infection are excluded from the study Sterile study equipment Study procedures are performed according to aseptic principles required during surgery and post-operative dressing changes IFU allows for the use of prophylactic, perioperative antibiotics as part of the surgical management process
Rejection / loss of graft	
 Cell material is autologous IFU reinforces use of aseptic principles Patient selection (i.e., exclusion of patients known to have a pre-existing condition that may interfere with wound healing)
Excessive bleeding at donor site	
 IFU details biopsy harvesting processes (including infiltration with adrenaline)
Lack of take of graft	
 IFU details wound site preparation requirements IFU contraindicates infection in wound site
Cross contamination	
 ReCell Device is single use and is marked as used at 5 minutes post incubation commencement preventing further restarts Only one vial of Trypsin is included with each device IFU details that ReCell is for autologous use only
Worsening Scar	
 IFU/protocol details instructions for proper dressing/management of treatment and donor wounds.
Risks related to Biopsy Processing	
Biopsy separation not possible	
 Trypsin extensively tested and released following assessment of activity Incubation of biopsy takes place at ~36.5°C which is within the optimal temperature for Trypsin activity IFU details troubleshooting strategies for difficult to separate biopsies IFU details procedures for harvesting suitable biopsies IFU details that Trypsin is to be reconstituted with Water For Injection (WFI) and warn that reconstitution with Compound Sodium Lactate for Irrigation (CSLI) may impact enzyme activity

Cell viability low	
 • IFU details that biopsy should not be exposed to Trypsin for longer than 60 minutes • IFU describes the cell scraping process to maximize cell quantity isolation • Conical well has been designed into processing unit to allow for maximal cell draw-up post filtration • Biopsy incubation occurs at ~36.5°C which is within the optimal temperature for Trypsin activity. Device is fitted with alerts if this temperature is exceeded
--------------------	---

Potential Risks	Mitigation Strategies
No or minimal epithelialization due to improper processing, cell suspension application, inadequate cell suspension volume or inadequate healing	
 • IFU detailing biopsy size requirements • IFU detailing biopsy processing steps and troubleshooting measures • IFU detailing correct cell dilution • IFU detailing maximum time frame for biopsy exposure to Trypsin • IFU detailing contraindications for biopsy sites such as infection • Patient selection excludes patients with pre-existing infections. • IFU detailing correct dressing materials to be used and time frames and processes for replacing dressings so as not to damage healing wounds on dressing removal • Patient selection (i.e., exclusion of patients known to have a pre-existing condition that may interfere with wound healing)
Risks related to cell application	
Nozzle blockage	
 • Nozzles designed with an aperture which allows for cells to pass through easily • 100 micron filtration occurs prior to spraying of cells • Spare nozzle supplied with each device
Nozzle aperture position	
 • IFU recommend test spray • IFU describes aperture positioning

The potential risks to the subject and adverse events associated with use of the ReCell Device discussed in the tables above are minor and easily controlled.

Adverse Event Evaluations and Reporting

Subjects will be monitored for safety from time of enrollment to conclusion of study visits. All adverse events will be collected by direct subject communication with investigator/study coordinator and review of source documents.

At each post-treatment visit, the research team will assess if the subject has experienced any adverse effects post-treatment with the investigational device. The subject will be asked if he/she has any problems, issues and/or concerns since the last encounter visit that could be potentially related to study participation. Any conditions or symptoms reported after the subject receives investigational product will be recorded as an adverse event (AE) on the AE eCRF. This includes new events after study device administration, conditions

that become more severe or increase in frequency, any disease-related signs or symptoms present at the Screening Pre-Treatment visit that have worsen in severity or frequency, as well as any event or finding that the Investigator feels is clinically significant.

Other treatment-related adverse events requiring surgical intervention prior to Week 12 post-treatment and all serious adverse event (SAE) occurrences will be treated and recorded in the eCRF. For all adverse events, the Investigator will provide an assessment of the event, its treatment resolution, and relationship to the investigational device. Subjects who have an ongoing AE related to the study device at Week 24 post-treatment will be followed for 30 days until resolution and/or stabilization of the event at a level acceptable to the Investigator.

Adverse Event Definitions:

Identification of Adverse Events (AEs), Adverse Device Effects (ADEs) An adverse event is defined as any new medical problem or exacerbation of an existing problem, experienced by a subject while enrolled in the study after receiving investigational product, whether or not it is considered related to the investigational device by the Investigator.

Treatment-Related Adverse Event

A treatment-related adverse event is an adverse event that is judged to be related to the investigational device, study therapy and study-related procedures.

Unexpected Adverse Event

An unexpected adverse event is any adverse effect which the frequency, specificity or severity is not consistent with the risk information described in the investigational plan.

Anticipated (Expected) Adverse Event

Potential adverse event that a subject may experience following the use of the ReCell device as described in this section above and using the potential risks listed in the above tables.

Definitions of Specific Major Treatment –Related Adverse Events:

Infection: The presence of infection for the ReCell treated areas and control site will be evaluated at each post-treatment visit. Infection will be evaluated in accordance with the Center for Disease Control (CDC) guidelines for nosocomial infections using standard clinical measures such as visual examination of the treatment sites for delayed healing, redness, inflammation and surrounding cellulitis. In the presence of symptoms (i.e., purulent exudate, changes in wound appearance such as hyperemia, and erythema in the uninjured skin surrounding the wound), infection will be confirmed using microbiological testing procedures and treatments initiated according to the institutions' infection management protocols, which will be recorded on the eCRF and Adverse Event form. Infection will be managed according to the standard protocols of the clinical site. For example, treatment of infection will involve the daily cleaning and dressing of wound sites until such time that the infection is clear. Treatment with broad spectrum antibiotics until microbiology sensitivities return from the testing laboratory is recommended. Upon return of sensitivities, antibiotic therapy may either continue as is, or be changed at the discretion of the investigator. All treatment regimens applied in the management of infection will be recorded on the eCRF.

Allergic Response to Trypsin: The allergic response to Trypsin, the enzyme used in the ReCell Device for disaggregation of the biopsy, will be evaluated. An allergic response to Trypsin is most likely to present as contact dermatitis (defined as an altered state of skin reaction induced by exposure to an external agent). Substances that produce this condition after single or multiple exposures may be irritating or allergic in nature and induce an inflammatory response. The most common clinical expression of this induced inflammation is dermatitis (eczema).

The evaluation tools for assessment of the allergic response to Trypsin have been developed in accordance with guidelines published in the Journal of the American Academy of Dermatology. The subject will be evaluated at each post-treatment visit for any occurrences of an allergic reaction (e.g. eczema/dermatitis). Any allergic response(s) to trypsin will be recorded in the eCRF and depending on severity, will have an additional reporting to the IRB, Research Monitor and study report.

The incidence of adverse response to Trypsin is expected to be low.

Other Treatment-Related Adverse Event Requiring Subsequent Surgical Intervention

Any treatment-related adverse event resulting in subsequent surgical intervention (e.g., “graft loss” requiring retreatment) will also be considered a major treatment-related adverse event.

The incidence of other treatment-related adverse events requiring subsequent surgical intervention is expected to be low.

Clinical investigators and ultimately the Principal Investigator will be responsible for AE identification, documentation, grading and assignment of attribution to the investigational device.

All observed or volunteered adverse effects (serious or non-serious) and abnormal test findings deemed clinically significant by the investigator, regardless of treatment group, if applicable, or suspected causal relationship to the investigational device or, if applicable, other study treatment or diagnostic product(s) will be recorded in the subjects’ eCRF. Criteria for grading of adverse events will be as defined by the Common Terminology Criteria for Adverse Events (CTCAE) version 4.0 (<http://www.upToDate.com/contents/common-terminology-criteria-for-adverse-events>). For all adverse effects, sufficient information will be pursued and/or obtained so as to permit 1) an adequate determination of the outcome of the effect (i.e., whether the effect should be classified as a *serious adverse effect*) and; 2) an assessment of the causal relationship between the adverse effect and the investigational device or, if applicable, the other study treatment or diagnostic product(s).

Severity

Each adverse event will be assessed for its severity, or the intensity of an event experienced by the subject, using the Common Terminology Criteria for Adverse Events (CTCAE), v4.0. The CTCAE grading (severity) scale will be utilized for each AE based on the following:

Grade 1 = Mild: Asymptomatic or mild symptoms; clinical or diagnostic observations only; intervention not indicated, discomfort noticed, but no disruption to daily activity

Grade 2 = Moderate: Minimal, local or noninvasive intervention indicated, discomfort sufficient to reduce or affect normal daily activity

Grade 3 = Severe: Medically significant but not immediately life-threatening; hospitalization or prolonged hospitalization indicated; disabling, inability to work or perform normal daily activity

Grade 4 = Life-threatening: Urgent intervention indicated

Grade 5= Death: Death related to an adverse event

Relationship of Adverse Events to the ReCell Investigational Device

The Investigator should assess the relationship of the adverse event to the investigational device. The relationship should be assessed using the following categories:

- **Definitely Related:**
A direct cause and effect relationship between the investigational device/treatment and the adverse event exists.
- **Likely Related:**
A direct cause and effect relationship between the investigational device/treatment and the adverse event has not been clearly demonstrated, but is likely or very likely.
- **Unlikely Related:**
A direct cause and effect relationship between the investigational device/treatment and the adverse event is improbable, but not impossible.
- **Unrelated:**
The adverse event is definitely not associated with the investigational device/treatment.

Outcome

The Investigator will categorize the outcome of the adverse event using the following definitions:

Resolved: The subject recovered from the adverse event.

Resolved with sequelae: The subject recovered, but with an after effect possibly due to disease, injury, treatment, or procedure.

Ongoing: At the time of the last assessment, the event is ongoing, with an undetermined outcome.

Death: The adverse event directly caused death.

Unknown: There is an inability to access the subject or the subject's records to determine the outcome (i.e., subject withdrew consent or is lost to follow-up)

Unanticipated Adverse Device Effects (UADEs)

An unanticipated adverse device effect is defined as “any serious adverse effect on

health or safety, or any life-threatening problem, or death caused by, or associated with, a device; if that effect, problem, or death was not previously identified in nature, severity, or degree of incidence in the investigational plan, or application (including supplementary application), or any other unanticipated serious problem associated with a device that relates to the rights, safety, or welfare of subjects.”

If an unanticipated adverse device effect occurs, the investigator must report the event promptly to the Sponsor, the IRB and Medical Research Monitor via email or telephone within 24 hours of first learning of the event. The Sponsor will conduct an evaluation of the unanticipated adverse device effect and will provide a written report the results to FDA and to all reviewing IRBs and participating investigators within 5 working days.

Such reports will also be promptly reported by [contact]), by email ([contact]), or by [contact]) to the Human Research Protection Office (HRPO). A complete written report should follow the initial notification (*Please refer to Section 6.4 below*)

Serious Adverse Events (SAEs)

Each adverse event should be assessed for its seriousness using the criteria outlined below. The term serious adverse event is not synonymous with a “severe” adverse event, which may be used to describe the intensity of an event experienced by the subject. An adverse event should be classified as an SAE if it meets any of the following criteria:

- Results in, or contributes to, a death
- Life-threatening (i.e., the subject was, in the opinion of the investigator, at risk of death at the time of the event, but it does not include an event that, had it occurred in a more severe form, might have caused death)
- Results in permanent disability or incapacity (i.e., permanent impairment of a body function or permanent damage to a body structure)
- Requires in-subject hospitalization or prolongs hospitalization
- Necessitates medical or surgical intervention to preclude a permanent disability or incapacity
- Results in a congenital anomaly or birth defect

Non-serious adverse events are all events that do not meet the criteria for a “serious” adverse event.

Deaths

The Principal Investigator must notify the IRB (via IRBNet) and the sponsor of the IDE within 24 hours of first learning of a subject’s death, regardless of whether the death is related or unrelated to the investigational device. The Investigator should attempt to determine, as conclusively as possible, whether the death is related to the device. The cause of death and the Investigator’s discussion regarding whether or not the death was device-related should be described in a written report. Serious adverse events must be reported even if the PI believes that the adverse event is unrelated to the protocol.

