5.3 Subject Population

The research population to be studied will include male or female military healthcare beneficiary of any race or ethnicity, aged 18 years or older, who is being treated for a traumatic wound at WRNMMC. With a target enrollment of 20 evaluable subjects, this investigation will include individuals treated for traumatic wounds at WRNMMC with full-thickness wounds, with loss of the dermis extending to deeper tissue layers and disrupting dermal blood vessels, and deep partial-thickness wounds, with injury limited to the epidermis and superficial dermis with no damage to the dermal blood vessels that were successfully treated with INTEGRA™ MBWM. Successful INTEGRA™ MBWM engrafting is defined as the presence of a contiguous vascularized granulation layer.

It is planned to enroll a sufficient number of subjects at WRNMMC in order to ensure a total number of 20 evaluable subjects. Therefore, up to 30 subjects will be consented and enrolled then screened to achieve a maximum of 20 evaluable subjects. Subjects who do not receive treatment with the assigned study device (ReCell) will be considered non-evaluable and therefore a screen failure for study participation.

WRNMMC will be the coordinating center for this clinical trial and will be the only site to enroll subjects for participation. The University of Pittsburgh, UPMC Center for Innovation in Restorative Medicine (CIRM), under the direction of Dr. [name] will be the Sponsor of the IDE and will also function as the Data Coordinating Center (DCC) accountable for maintaining oversight of all data management activities to ensure quality and integrity with accurate reporting, interpretation and verification, and will ensure systems and procedures are in place for the protection and safeguarding of the confidentiality of all data records.

It is anticipated the availability of the study population will be derived from the investigators' clinical practices, individuals evaluated and/or referred by healthcare providers aware of the study within the WRNMMC Orthopaedic Surgery, Plastic Surgery and General Surgery Clinics. Additionally, study participants will be recruited by use of a posting on the research registry at www.clinicaltrials.gov. Those interested

in study participation will be instructed to contact a study team member. This study will not use any advertisements, flyers or brochures.

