Subjects will be anesthetized and the wound will be prepared according to hospital standard of care practices. It is anticipated that the total surgical time will be up to 3 hours. The operative procedure will be performed by the PI and/or the Co-PI in the operating room at WRNMMC. The INTEGRA™ MBWM treated wound will be sectioned into two **similarly sized** study regions up to 320cm² each, the upper limit of application area for one ReCell kit. The surgeon will label these two regions “A” and “B” with a surgical pen. A pre-generated randomization envelope will then be opened to determine which area will be the control area and which area will be treated with ReCell. Any wound area outside the study regions will be treated according to standard of care.

In this study, serial histology assessments of the wound site will be made. Baseline punch biopsies of 3 mm diameter tissue samples from the INTEGRA™ MBWM treated wound site and adjacent normal skin will be obtained in the operating room prior to start of the surgical procedure. This baseline histological analysis will examine the vasculogenesis and cytology of the regenerate before ReCell treatment. The biopsy procedure will be recorded in the eCRF.

A digital photograph will be taken of the control and ReCell sites (“A” region and “B” region) and noted on the eCRF. Next, the wound bed will be gently scrubbed and “prepared” then the thin silicone layer is removed, the wound bed will be prepped and prepared again for receipt of proposed STSG or STSG in conjunction with ReCell regenerative skin treatment system.

Harvesting of autograft will be the same thickness for both control and investigational site; at a depth of 0.012 inch to 0.016 inch which is alignment with standard of care practice. Donor tissue for the STSG for the ReCell treatment area may be harvested from the same area as for the control STSG or separate area. To assess healing of the donor sites for ReCell, the site has to be at a discrete location, but can be collocated, i.e. same thigh, but different area.

A digital photograph will be taken of donor sites following tissue removal and will be noted in the eCRF. These and all subsequent photographs at each study visit will be taken in ambient light, with a consistent background and distance between camera and subject.

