For this 2 x 7 mixed design (i.e., two treatment groups x 7 waves of measurements) with a continuous level outcome, a two-way (completely within) repeated measures ANOVA will be performed with the overarching objective being the test of significance for the two-way treatment x time interaction (using $\alpha = .05$). If the two-way interaction is significant, simple effects analysis will be performed so as to assess at which time point significant differences for the treatment variable are obtained. Moreover, if the first order interaction is significant, trend analysis will be conducted in an effort to uncover any nonlinear patterns across time (up to polynomial $t - 1$, where $t = \text{time}$). Graphic displays will be provided so as to illuminate the nature of the findings and the between treatment trajectories.

All assumptions will be examined, including sphericity and homogeneity of variance/covariance matrices and any data anomalies (e.g., outliers) will be examined and treated accordingly. It should be kept in mind that given the small sample size ($n = 20$), there may still be substantive effects despite non-significant results, hence univariate and multivariate effect sizes will be reviewed (e.g., partial η^2).

There are many techniques beyond a mixed ANOVA approach that can more dynamically model the longitudinal nature of this design, such as multilevel modeling, generalized estimating equations, and/or latent growth curve modeling. However, those techniques will need to be deferred until a larger sample size is obtained. All analysis will be conducted using SPSS 21.0 or Stata 11.0.

Analysis Sets of ReCell Device Treatment vs. Control Comparison:

Safety Analysis Set:

The safety analysis population will include all enrolled subjects. Data will be analyzed based on treatment received. The number and percentage of subject who discontinued the study due to adverse event will be provided. Also, descriptive statistics, as

appropriate, will be provided for the following, by treatment:

- Delayed healing/non-healing of wound and donor site
- Graft loss
- Heterotopic ossification
- Infection
- Scar contracture
- Durability (i.e. abrasions/injuries at graft site due to graft fragility)
- Allergic response to trypsin
- Subject Complaint (pain and itching)
- Vital Signs
- Blood chemistries and hematology

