- i) Pre-treatment (baseline) biopsies at Integra area and of adjacent normal skin; then at Weeks 2, 4, 12 post-treatment, biopsies will be taken from the ReCell and Control treated sites.
- j) Photos will be taken at following time points: PRE-TREATMENT- Control and ReCell sites (“A” region and “B” region); Donor sites (ReCell, 1:1.5 and 1:5 meshing) following tissue removal, at treatment wound area prior to primary dressing placement and of the ReCell donor site, control area and ReCell treated area at each post-treatment visit for assessment of healing process
- k) ReCell donor tissue harvested for cell suspension; donor tissue harvested for STSG Control area (meshed at 1:1.5) and donor tissue for the ReCell treatment area (meshed at 1:5 mesh)
- l) Assessments made for: Atypical healing and/or delayed healing/non-healing, graft loss, heterotopic ossification, infection scar contracture, durability (i.e. abrasions/injuries at graft site due to fragility), allergic response to trypsin
- m) Subject to complete “patient” part of POSAS at all post-treatment study visits. Full POSAS (including patient and two independent observers) completed at Week 12 and 24 post-treatment
- n) Concomitant medication use (excluding anesthetic regimen) and all treatment regimens applied in the management of infection during the acute healing phase
- o) AEs assessed from time of enrollment through study completion (Week 24) including AEs related to treatment requiring surgical intervention prior to Week 12 post-treatment and all serious adverse event occurrences

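### Adverse events start after the investigational product in one place and at enrollment in another, so early events may be misclassified in the safety tables, and untreated subjects sit in a denominator where they cannot have an event

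*Combined protocol and SAP*

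**What the plan says.** The plan contains two start points for adverse events.

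**After the product.** The formal definition (section 6.2, Adverse Event Definitions) covers a problem "experienced by a subject while enrolled in the study after receiving investigational product". The recording rule for the case report form appears in section 5.5.4 (screening assessments) and twice in section 6.2. It reads "Any conditions or symptoms reported after the subject receives investigational product will be recorded as an adverse event (AE"), and goes on to include anything the investigator considers clinically significant.

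**From enrollment.** Section 6.2 also says, twice, "Subjects will be monitored for safety from time of enrollment to conclusion of study visits". The schedule of assessments at the end of the appendices ticks adverse events at Screening and in the operating room, and its footnote o reads "AEs assessed from time of enrollment through study completion (Week 24) including AEs related to treatment requiring surgical intervention".

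**Analysis set.** Section 5.7.3 says "The safety analysis population will include all enrolled subjects", with data analyzed by treatment received. Section 5.3 says "up to 30 subjects will be consented and enrolled then screened to achieve a maximum of 20 evaluable subjects". It classes subjects who do not receive ReCell as non-evaluable screen failures.

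**The concern.** Safety and tolerability are the primary outcome (section 5.7.1), reported descriptively in about 20 treated subjects, so one subject moves a rate by 5 percentage points. The list includes treatment-related adverse events requiring surgery before Week 12 and all serious adverse events. Both are subsets of adverse event as section 6.2 defines it, so both inherit its start point.

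Subjects undergo study procedures before that point. The baseline punch biopsies of the wound and normal skin "will be obtained in the operating room prior to start of the surgical procedure". General anesthesia, both graft harvests and the ReCell donor shave also come before the suspension is applied. Section 5.6.2 calls the operation a research procedure. The definition of a treatment-related adverse event expressly covers study-related procedures, yet its parent definition excludes events during those done before application.

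At stake are which events enter the tables in section 5.7.3, and whether numerator and denominator describe the same subjects.

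**Working it through.** The plan states no figure on this point, so there is none to reproduce. The check is mainly a comparison of texts, followed by simple ratios.

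**1. What each rule turns on**

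- Formal definition (6.2): when the event is *experienced*; it must follow the product.
- Recording rule (5.5.4 and 6.2): when the event is *reported*; the report must follow the product, but onset may be earlier.
- Monitoring statement (6.2) and footnote o of the schedule: enrollment onwards.

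So there are three criteria. An intraoperative event before application fails the first, may pass the second if mentioned at Week 1, and passes the third. I read receipt of the product as application of the suspension, because the recording rule goes on to speak of events after device administration.

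**2. What lies before application (5.5.4)**

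- Screening, up to 30 days before treatment. Follow-up is 24 × 7 = 168 days, so this is at most 30 / (30 + 168) = 15.2% of a treated subject's time.
- In the operating room: anesthesia, baseline punch biopsies, graft harvests, and the donor shave (step 1 of the ReCell procedure; application is step 6).

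**3. Which outcomes depend on the start point**

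- Little affected: wound and donor-site healing, graft loss, infection, contracture, durability and trypsin response, which are assessed at post-treatment visits whatever the adverse event window.
- Affected: serious adverse events, treatment-related events needing surgery, and the adverse event tabulations in 5.7.3.

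**4. How often an affected event might occur**

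The only rates are the risk categories in 6.2. With n subjects each exposed once at rate p, P(at least one) = 1 − (1 − p)^n.

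- Anesthesia complications, below 1%: with p = 0.01 and n = 20, 1 − 0.99^20 = 18.2%, an upper limit.
- Blood-draw or punch-biopsy discomfort, bruising or bleeding, 5% to under 10%: from 1 − 0.95^20 = 64.2% (n = 20) to 1 − 0.90^30 = 95.8% (n = 30), or about 1 to 3 subjects expected.

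The second range overstates the early risk, because the category pools blood draws with all biopsies, including those after treatment. Minor events of this kind would affect only the general tables, not the serious-event or surgery component.

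**5. The denominator**

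Let u be the number enrolled but never treated. With 20 treated and a ceiling of 30 enrolled, u runs from 0 to 10. At u = 10, 10 / 30 = 33.3% of the safety set has no time in which an adverse event can occur under the formal definition. With k affected subjects, the rate is k / (20 + u). The values of k are assumptions.

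| k | u = 0 | u = 5 | u = 10 |
|---|---|---|---|
| 1 | 5.0% | 4.0% | 3.3% |
| 2 | 10.0% | 8.0% | 6.7% |
| 4 | 20.0% | 16.0% | 13.3% |

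The relative reduction is u / (20 + u), so at most one third.

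**The case against.** The strongest reply is that the data are largely collected anyway.

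- The recording rule turns on reporting, so a biopsy bleed mentioned at Week 1 is recorded.
- Section 5.5.4 (Histological methods) has the coordinator telephone within 72 hours of a biopsy.
- Section 5.5.5 collects device-related and surgical problems from the operation.
- Section 6.2 sends all observed or volunteered adverse effects to the case report form, with no start time given.
- Deaths (6.2) and serious events in enrolled subjects (6.4) must be reported to the IRB and the sponsor.
- Biopsies, harvests and application share one operation of up to 3 hours, so infection or delayed donor healing would appear after application.

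All of this stands. A reader might infer that harms from research procedures before ReCell vanish from the primary safety outcome. The documents do not support that: most listed outcomes do not depend on the adverse event window, and most procedural harms would be seen. But collecting an event or reporting it to the IRB does not settle whether it counts in the tables, and none of these provisions amends the definition.

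It can also be said that the denominator is a separate problem, which a new start date alone would not cure. That is right. Analysis by treatment received may be meant to leave out untreated subjects, who received neither treatment, but section 5.7.3 does not say so. The sample case report forms and the data management plan are listed as appendices without their content, so any onset field there could not be checked.

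**Conclusion.** The inconsistency is real and unresolved in the current text. Its likely effect is narrow: misclassification in the adverse event tables, and possible omission from the serious-event and surgery component of events that arise before application or occur in enrolled subjects never treated. Section 6.2 itself lists failure to separate the biopsy as a risk. If no suspension could then be applied, that subject would have had anesthesia, biopsies and a donor shave, yet could have no adverse event by definition.

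The denominator mismatch is a second, separate defect. It lowers stated rates by nothing if everyone enrolled is treated and by one third at the enrollment ceiling. A reader might take 20% falling to 13.3% as a forecast. It is not: four affected subjects and ten untreated are assumptions, the latter the worst case when 20 are treated.

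This should be corrected because it changes which events and rates enter the primary safety tables. It does not call the trial's design into question.

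**What to change.** Reconcile the adverse event wording in section 5.5.4 (screening), section 6.2 (opening text, evaluations and reporting, and definitions) and the schedule with its footnote o to one window: consent/enrollment through Week 24.

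Mark each event by onset date as before or after ReCell application. In section 5.7.3, report post-ReCell event rates with treated subjects as the denominator, and tabulate or list pre-application events separately, including those in subjects never treated. A single before/after mark is enough for a descriptive study of this size.

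The cost is protocol wording and one derived field. Slightly more events will be recorded, and some stated rates will be higher because untreated subjects leave the denominator.
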